3 OBJECTIVES AND ENDPOINTS

3.1 Objectives, Hypotheses, and Estimands

Primary

The primary objective is to assess the safety and efficacy of ABBV-154 versus placebo in subjects with PMR, who are dependent on treatment with glucocorticoids with doses of at least 5 mg/day prednisone equivalent (glucocorticoid-dependent PMR).

- **Primary Efficacy Objective:** The primary efficacy objective of the study is to demonstrate that ABBV-154 treatment results in a longer disease-free time when compared with placebo treatment in the Intent-to-Treat (ITT) population, which consists of all randomized subjects with at least one dose of study drug.

The hypothesis corresponding to the primary efficacy objective is that the time to flare with ABBV-154 treatment is longer than that with placebo treatment. The estimand for the primary endpoint is defined as the median time to flare in the study for each ABBV-154 group versus the placebo group in the ITT population. Subjects will be censored at the time of the last available assessment, initiation of immunomodulator, or violation of protocol-allowed systemic glucocorticoid use.

- Secondary Efficacy Objectives: The secondary efficacy objectives of the study are to demonstrate greater efficacy with ABBV-154 treatment when compared with placebo treatment with respect to the secondary endpoints specified in Section 3.3, in the ITT population.

The estimands corresponding to the secondary efficacy objectives are:

- For each binary secondary endpoint: The difference in percentage of subjects achieving a response for each ABBV-154 group versus the placebo group in the ITT population.
- For each continuous endpoint: The mean difference between each ABBV-154 group versus the placebo group in the ITT population.

Secondary

The secondary objective is to assess the pharmacokinetics (PK), pharmacodynamics (PD), and immunogenicity of ABBV-154.

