7.4 Statistical Analyses for Efficacy

Efficacy analysis will be performed by the subject's randomized treatment group. All statistical tests will be performed at a 2-sided significance level of 0.1. A 95% confidence interval (CI) of the treatment difference between each ABBV-154 dose and placebo will be provided. The actual value of stratification factors will be used in the analysis. Enrollment in the optional PK sampling is not expected to impact any of the efficacy endpoints and will thus not be used as a stratification factor in the analysis.

- For time-to-event endpoints, comparison of number of events will be made between each ABBV-154 dose and placebo based on log-rank test stratified by stratification factors. The point and CI estimate of median time to event and event-free rate for each group will be reported based on Kaplan-Meier curves. Hazard ratio and its corresponding CI for each ABBV-154 group compared with placebo will be estimated using Cox regression analysis adjusting for stratification factors. For all analyses of time-to-event endpoints, subject without an event at the time of the analysis will be administratively censored at the time of the last available assessment.
- For categorical variables, pairwise comparison will be made between each ABBV-154 dose and placebo using the Cochran-Mantel-Haenszel (CMH) test, adjusting for stratification factors. Nonresponder imputation incorporating multiple imputation (NRI-MI) to handle COVID-19 will be the primary approach to handle missing data for categorical endpoints.
- For continuous variables other than glucocorticoid dose, the comparison will be made between each ABBV-154 dose and placebo based on the mixed effect model repeated measures (MMRM) adjusting for visit, interaction between treatment and visit, actual values of stratification factors as fixed factors, and baseline value as a covariate. The MMRM will be the primary approach to handle missing values for continuous endpoints.
- For analyses of glucocorticoid dose, comparison will be made between each ABBV-154 dose and placebo based on the analysis of covariance (ANCOVA) adjusting for stratification factors as fixed factors, and baseline glucocorticoid dose as a covariate.

Summary and Analysis of the Primary Endpoints

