### **8.0 Handling of Potential Intercurrent Events for the Primary and Secondary Endpoints**

The primary efficacy endpoint (defined in Section 3.1) will be analyzed based on the ITT population and subjects will be censored at the time of the last available assessment, initiation of immunomodulator, or violation of protocol-allowed systemic glucocorticoid use.

The categorical secondary efficacy endpoint (defined in Section 3.2) will be analyzed based on the ITT population and the following methods will be used to address the potential intercurrent events:

- Subjects will be considered as not achieving the response after the initiation of rescue medication, immunomodulator or violation of protocol-allowed systemic glucocorticoid use.

The continuous secondary efficacy endpoints (defined in Section 3.2) will be analyzed based on the ITT population and the following methods will be used to address the potential intercurrent events:

- No intercurrent event will be considered in the analysis of glucocorticoid dose.

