## **9.0 Efficacy Analyses**

### **9.1 General Considerations**

All efficacy analyses will be conducted in the ITT Population in each period. In addition, Per-protocol analysis for the primary endpoint will be performed. All tests will be 2-sided at an alpha level of 0.1.

The Primary Analysis will be performed after all subjects have either completed the Week 24 visit or withdrawn from the study. This analysis will be the only and final analysis for the primary and secondary efficacy endpoints.

The primary endpoint will be analyzed using logrank test stratified by baseline stratification factors [Glucocorticoid use at Baseline ( $\geq 10$  mg/day;  $< 10$  mg/day prednisone equivalent); Length of prior glucocorticoid treatment for PMR ( $\leq 1$  year;  $> 1$  year)]. The point and 95% confidence interval (CI) estimate of median time to event and event-free rate for each group will be reported based on Kaplan-Meier curves. Hazard ratio and its corresponding 95% CI for each ABBV-154 group compared with placebo will be estimated using Cox regression analysis adjusting for Baseline stratification factors [Glucocorticoid use at Baseline ( $\geq 10$  mg/day;  $< 10$  mg/day prednisone equivalent); Length of prior glucocorticoid treatment for PMR ( $\leq 1$  year;  $> 1$  year)]. For all analyses of time-to-event endpoints, 1) subject without an event at the time of the analysis will be administratively censored at the time of the last available assessment or cutoff, whichever is later; 2) a flare at Baseline will not be counted as an event; 3) if a flare event and an intercurrent event happen on the same day, subject will be counted as having a flare event.

Unless otherwise specified, the categorical endpoints and continuous endpoints will be analyzed by Cochran-Mantel-Haenszel (CMH) and Mixed-Effect Model Repeat

Measurement (MMRM), respectively, and the corresponding analyses are specified in Section 9.2.

Unless otherwise specified, any subject who is randomized based on a wrong stratum will be analyzed according to the actual stratum the subject belongs to.

"Baseline" refers to the last non-missing observation on or before the day of the first administration of study drug or randomization if no study drug is given. Observation on the same day as the first administration of study drug will be considered for the baseline, regardless of whether observation time (if available) was before or after the first administration of study drug time.

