## **9.2 Handling of Missing Data**

For time-to-event endpoints, event and censoring details will be described in Section 9.3.

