**Table 1. Summary of the Estimand Attributes of the Primary Efficacy Endpoint(s)**

Estimand Label	Attributes of the Estimand				Statistical Summary
	Treatment	Endpoint	Population	Handling of Intercurrent Events (IE)	
Primary: Time to flare (Composite)	ABBV-154 vs. Placebo	Time to flare	ITT	IE1: at the time of immunomodulator initiation  IE2: at the time of violation of protocol-allowed systemic glucocorticoid use  Subjects will be censored at the time of intercurrent event.	Between ABBV-154 and placebo: difference in number of events, difference in median time to event, event-free rate difference, hazard ratio and its corresponding CI

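### SAP 9.1 keeps subjects who leave event-free at risk until an undefined cutoff, contradicting the last-assessment censoring stated in four other places

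*SAP*

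**What the plan says.** SAP 9.1 covers all time-to-event analyses and has a subject without an event "administratively censored at the time of the last available assessment or cutoff, whichever is later". The word cutoff appears nowhere else in either document.

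Four other places give a different rule:

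- Protocol 7.4, in nearly the same sentence but without the cutoff: "subject without an event at the time of the analysis will be administratively censored at the time of the last available assessment".
- Protocol 3.1, within the primary estimand: "Subjects will be censored at the time of the last available assessment, initiation of immunomodulator, or violation of protocol-allowed systemic glucocorticoid use".
- SAP 2.1, which repeats the Protocol 3.1 sentence.
- SAP 8.0: "subjects will be censored at the time of the last available assessment, initiation of immunomodulator, or violation of protocol-allowed systemic glucocorticoid" use.

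SAP 9.2 points elsewhere for the detail: "For time-to-event endpoints, event and censoring details will be described in Section 9.3". Section 9.3 does not supply it. Section 9.3.2 names the test and its strata, and Table 1 covers intercurrent events only: "Subjects will be censored at the time of intercurrent event". On timing, SAP 9.1 says "The Primary Analysis will be performed after all subjects have either completed the Week 24 visit or withdrawn from the study", which fixes when the analysis happens but gives no data cutoff date.

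**The concern.** Censoring should remove a subject from the risk set when observation ends. Taking the later of the last assessment and a cutoff does the reverse. A subject who withdraws or is lost without a flare stays in the denominator until the cutoff, although no flare can be recorded for them. Subjects who have already flared, or who are censored at an intercurrent event, are not affected.

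Three results are at stake:

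- **Kaplan-Meier flare-free rates and medians** are inflated in any arm with event-free dropout. The primary estimand is itself framed as median time to flare.
- **The hazard ratio** is pulled slightly toward 1 if the drug works and dropout is equal. If dropout differs by arm, it can move either way.
- **The log-rank level** is at risk only when dropout differs by arm.

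The plan would not reveal the problem. SAP 9.3.3 lists no sensitivity analysis for the primary endpoint, and the per-protocol analysis would inherit the same rule. The binary flare-free endpoint treats early withdrawal as non-response (SAP 9.2.2). The same leaver would therefore be flare-free to the cutoff in the primary analysis and a failure in the secondary one.

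**Working it through.** **1. The plan's own figure.** SAP 2.4 assumes 30% (placebo) and 70% (340 mg) flare-free at Week 36, 37 flares and two-sided alpha 0.1.

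- HR = ln(0.70)/ln(0.30) = 0.296.
- Schoenfeld power = Φ(√(37 × 0.25) × |ln 0.296| − 1.645) = Φ(3.703 − 1.645) = 0.980.

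This agrees with the stated power of more than 90%, which is not in dispute.

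**2. Kaplan-Meier bias in closed form.** Assume constant hazards and independent dropout.

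- Placebo λ = −ln(0.3)/36 = 0.03344 per week; 340 mg λ = −ln(0.7)/36 = 0.00991.
- Dropout of 20% by Week 24 (assumed): h = −ln(0.8)/24 = 0.00930.
- True Week 24 flare-free rate: exp(−24λ) = 0.448 placebo, 0.788 at 340 mg.
- Rate when event-free leavers stay at risk: 1 − [λ/(λ+h)] × [1 − exp(−24(λ+h))].
  - Placebo: 1 − 0.7825 × (1 − 0.3585) = 0.498.
  - 340 mg: 1 − 0.5159 × (1 − 0.6307) = 0.809.
- Placebo with 5% or 10% dropout: 0.460 or 0.473.
- Share leaving event-free by Week 24, [h/(λ+h)] × [1 − exp(−24(λ+h))]: placebo 0.2175 × 0.6415 = 14%; 340 mg 0.4841 × 0.3693 = 18%.
- Placebo median: true value ln 2/0.03344 = 20.7 weeks. Under SAP 9.1 with 20% dropout, solve 0.7825 × [1 − exp(−0.04274t)] = 0.5. Then exp(−0.04274t) = 0.361 and t = 23.8 weeks.

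These results are the same for all three meanings of cutoff below, because each keeps leavers at risk to at least Week 24.

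**3. Test and hazard ratio by simulation.** The model has 40 per arm, the hazards above, exponential dropout, accrual uniform over 52 weeks (assumed) and follow-up capped at Week 52. It uses an unstratified log-rank test at two-sided 0.1 and a Cox hazard ratio, with 8,000 trials per case. The simulation standard error is √(0.1 × 0.9/8000) = 0.3 points for a 10% rate. Three meanings of cutoff were tried:

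- (a) the calendar date of the last subject's Week 24;
- (b) Week 24, with follow-up truncated there;
- (c) the later of the last assessment and the subject's own Week 24.

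No true effect:

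| Dropout by Week 24, active / placebo | HR (a), (b), (c) | Trials favouring drug (nominal 5%) | Total rejection (nominal 10%) |
|---|---|---|---|
| 10% / 5% | 0.95, 0.97, 0.98 | 7.7%, 6.1%, 6.0% | 10.2%, 10.0%, 9.8% (separate run) |
| 20% / 10% | 0.89, 0.94, 0.95 | 11.1%, 7.7%, 7.0% | 13.4%, 11.2%, 10.6% |
| 30% / 10% | 0.79, 0.87, 0.90 | 20.6%, 11.0%, 10.2% | 21.1%, 12.8%, 12.2% |

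Last-assessment censoring in the same three cases gives HR 1.00 to 1.01, with 4.8% to 5.2% of trials favouring the drug. With equal 20% dropout, the SAP 9.1 rule gives HR 1.00 and total rejection of 10.6% to 11.0%, against 10.8% with last-assessment censoring.

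Design effect (true HR 0.296):

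| Dropout by Week 24, active / placebo | HR (a), (c) vs last assessment | Power (a), (c) vs last assessment |
|---|---|---|
| 20% / 20% | 0.31, 0.29 vs 0.29 | 96.8%, 97.8% vs 98.1% |
| 10% / 25% | 0.37, 0.31 vs 0.29 | 90.3%, 96.0% vs 97.8% |

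**4. Independent check.** A second simulation with 400,000 per arm, under meaning (b), gave matching results. With 20% dropout in both arms, flare-free rates were 49.7% and 81.0%. With no true effect and dropout of 30% active and 10% placebo, HR was 0.87 and total rejection 12.9%.

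**The case against.** The strongest reply is that SAP 9.1 is the later and more specific text. The SAP version history says the censoring detail was added there in version 2.0, so it could be said to govern. That does not rescue the plan: if SAP 9.1 governs, the biased rule applies, and SAP 2.1 and 8.0 of the same version still say otherwise. Three of the four conflicting places share essentially one clause, and the last words of the SAP 9.1 rule may be a slip for the earlier of the two dates. The documents do not show that, so the text still has to be corrected.

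The points about size largely stand:

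- The documents give no dropout rate and no reason to expect a large imbalance.
- Protocol 5.6 encourages subjects who stop study drug to keep attending visits, and intercurrent events censor at their own date. The affected group is only those who leave the study event-free with no earlier intercurrent event.
- With equal dropout the primary test is barely touched, and power stays above 90%.
- Under mild imbalance (10% against 5%) total two-sided rejection is nominal, and only its direction shifts. A clear two-sided excess needs meaning (a) or a large imbalance.
- Meaning (b) adds a truncation that the SAP does not state. Meaning (c) is the more literal use of a Week 24 cutoff and the mildest case.
- If cutoff meant each subject's own end of participation, the effect would nearly vanish. The text does not say this.
- The simulation is unstratified and treats flares as continuously observed, so it is idealised.

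This is also a Phase 2 study without overall Type I error control. Each comparison is nevertheless tested at 0.1, and the flare-free rates and medians will be reported for each arm.

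**Conclusion.** The concern holds. The plan gives two incompatible censoring dates for its primary endpoint. The one in SAP 9.1 rests on an undefined term and, read literally, credits unobserved time as flare-free.

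The inconsistency is certain from the text. The numerical effect is conditional on assumed dropout and accrual and on constant hazards. The inflation of flare-free rates does not need imbalance: it is about 1 to 5 percentage points for placebo at Week 24 with 5% to 20% dropout. Material distortion of the hazard ratio or the test does need dropout that differs by arm, and it depends on what cutoff means. Last-assessment censoring removes this particular bias, provided dropout is unrelated to flare risk.

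The correction belongs before unblinding for the Primary Analysis. Otherwise two programmers could derive different primary results from the same documents, and the choice between them could be made with the data in view.

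**What to change.** In SAP 9.1, item 1:

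1. Define the cutoff date.
2. Replace the later-of rule with censoring at the last available assessment of that endpoint (for the primary endpoint, the last flare assessment) on or before the cutoff date.
3. State that starting an immunomodulator, or breaching the systemic glucocorticoid rules, before a flare still censors at its own date.

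Repeat this rule in SAP 9.3.2 and Table 1, where SAP 9.2 sends the reader, so that these sections agree with SAP 2.1 and 8.0 and Protocol 3.1 and 7.4. Once censoring is at the last assessment on or before the cutoff, the bias described here goes away under any definition of the cutoff.

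The cost is a few lines of SAP text and the matching change to the censoring derivation. No new data are needed.

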3.4 Additional Efficacy Endpoints

All secondary endpoints will be analyzed at all visits other than those listed. In addition, the following endpoints will be analyzed at all visits assessed, per [Appendix F](#):

- Time to disease flare defined as Polymyalgia Rheumatica Activity Score (PMR-AS) increased from Baseline by ≥ 6.6 .
 - $\text{PMR-AS} = \text{high-sensitivity CRP (hsCRP) (mg/dL)} + \text{Patient Assessment of Pain Severity (numeric rating scale [NRS], 0 – 10)} + \text{Physician Global Assessment of Disease Activity (NRS, 0 – 10)} + (\text{morning stiffness duration [MST] in minutes} \times 0.1) + \text{elevation of upper limbs (EUL) (scale of 3 – 0)}$
- Time to disease flare defined as $\text{PMR-AS} \geq 9.35$
- Achievement of $\text{PMR-AS} < 1.5$
- Achievement of $\text{PMR-AS} < 7$
- Achievement of $\text{ESR} \leq 30 \text{ mm/h}$ at Week 24
- Achievement of $\text{hsCRP} \leq \text{upper limit of normal (ULN)}$ at Week 24
- Change from Baseline in hsCRP
- Change from Baseline in PMR-AS
- Change from Baseline in MST
- Change from Baseline in EUL
- Change from Baseline in Physician Global Assessment of Disease Activity NRS
- Change from Baseline in Patient Assessment of Pain Severity NRS
- Change from Baseline in Patient Assessment of Stiffness Severity NRS
- Change from Baseline in Functional Assessment of Chronic Illness Therapy-Fatigue (FACIT-Fatigue)
- Change from Baseline in Health Assessment Questionnaire Disability Index (HAQ-DI)
- Change from Baseline in Patient-Reported Outcomes Measurement Information System (PROMIS) Item Bank v 1.0 – Sleep Disturbance
- Change from Baseline in Patient Assessment of Bruising Severity NRS
- Change from Baseline in EuroQoL 5-dimension questionnaire, 5-level (EQ-5D-5L)
- Change from Baseline in Physician Assessment of Bruising Severity NRS
- For subjects participating in the Wearable Device Substudy:
 - Change from Baseline in the following sleep parameters: total sleep time, wake after sleep onset, sleep efficiency, and sleep onset latency
 - Change from Baseline in upper limbs range of motion (UL-ROM)

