5 STUDY ACTIVITIES

5.1 Eligibility Criteria

Subjects must meet all of the following criteria in order to be included in the study. Anything other than a positive response to the questions below will result in exclusion from study participation. Additional information on screening (including re-screening) can be found in the Operations Manual ([Appendix H](#)).

Consent

- ✓ 1. Subjects must be able to understand and willing to adhere to all protocol requirements and voluntarily sign and date an informed consent, approved by an independent ethics committee (IEC)/institutional review board (IRB), prior to the initiation of any screening or study-specific procedures.

Demographics and Laboratory Assessments

- ✓ 2. Adult **male or female, at least 50 years** of age at the time of screening.
- ✓ 3. Body mass index (BMI) is ≥ 18.0 to ≤ 39.9 kg/m² after rounding to the nearest tenth. BMI is calculated as weight in kg divided by the square of height measured in meters.
- ✓ 4. **Laboratory values** must meet the following criteria within the Screening Period prior to the first dose of study drug:
 - Serum aspartate aminotransferase (AST) $\leq 2.5 \times$ ULN;
 - Serum alanine transaminase (ALT) $\leq 2.5 \times$ ULN;
 - Estimated glomerular filtration rate (GFR) by simplified 4-variable Modification of Diet in Renal Disease (MDRD) formula ≥ 30 mL/min/1.73 m²;
 - Absolute neutrophil count (ANC) $\geq 1,500/\mu\text{L}$;
 - Absolute lymphocyte count $\geq 800/\mu\text{L}$;
 - Platelet count $\geq 75,000/\mu\text{L}$;
 - Glycated hemoglobin (HbA1c) $\leq 8.5\%$;
 - Serum potassium > 3.0 mmol/L and < 5.5 mmol/L; and
 - Thyroid-stimulating hormone (TSH) < 10 mIU/L.
- ✓ 5. Subject must have a negative test result for anti-citrullinated protein (anti-CCP) at Screening.

Disease Activity

- ✓ 6. Clinical diagnosis of PMR and fulfillment of the 2012 EULAR/ACR provisional classification criteria for PMR (see [Appendix D](#)).¹⁵ If utilizing the optional ultrasound criteria, ultrasound must have been assessed by a qualified physician experienced in musculoskeletal ultrasound.
- ✓ 7. Following a confirmed diagnosis of PMR, subject must have shown a clinical response to prednisone (or equivalent).

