- ✓ 8. Subject must have had at least 2 episodes of unequivocal PMR flare while attempting to taper prednisone, with the dose of prednisone (or equivalent) at the time of flare ≥ 5 mg/day, prior to Baseline; the most recent flare must have been within 24 weeks of Baseline. Unequivocal PMR flare is defined as clinical signs and symptoms of PMR (shoulder and/or hip girdle pain with inflammatory stiffness, neck pain with inflammatory stiffness, or new or worsened limited range of motion of hips and/or shoulders) that resulted in an increase in glucocorticoid dose.

- ✓ 9. Subject must not exhibit clinical signs and symptoms of PMR (shoulder and/or hip girdle pain with inflammatory stiffness, neck pain with inflammatory stiffness, or new or worsened limited range of motion of hips and/or shoulders) within 2 weeks of Baseline.

Subject History

- ✓ 10. Subject is judged to be in good health as determined by the Principal Investigator, based upon the results of medical history, laboratory profile, physical examination, chest x-ray (CXR), and a 12-lead ECG performed during Screening.
- ✓ 11. No history of an allergic reaction or significant sensitivity to constituents of the study drug (and its excipients) and/or other products in the same class. No history of anaphylactic reaction to any agent (e.g., food products and bee sting); or a reaction to any immunoglobulin G (IgG) containing product.
- ✓ 12. Subject must have no current or past history of infection including:
 - Active tuberculosis (TB) or meets TB exclusionary parameters (specific requirements for TB testing are provided in the Operations Manual);
 - Subjects **in Japan** only: Positive result of beta-D-glucan (screening for *Pneumocystis jirovecii* infection) or two consecutive indeterminate results of beta-D-glucan during the Screening Period.
 - Human Immunodeficiency virus (HIV) infection defined as confirmed positive anti-HIV antibody (HIV Ab) test;
 - Active infection(s) requiring treatment with intravenous anti-infectives within 30 days, or oral/intramuscular anti-infectives within 14 days prior to the first dose of study drug;
 - Chronic recurring infection and/or active viral infection that, based on the investigator's clinical assessment, makes the subject an unsuitable candidate for the study;

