### 3.3 Other Efficacy Endpoint(s)

The primary and/or secondary efficacy endpoints are listed in Section 3.1 and/or Section 3.2, respectively. All secondary endpoints will be analyzed at all visits other than those listed. In addition, the following endpoints will be analyzed at all visits assessed when applicable:

- Time to disease flare defined as Polymyalgia Rheumatica Activity Score (PMR-AS) increased from Baseline by  $\geq 6.6$ .
  - $\text{PMR-AS} = \text{high-sensitivity CRP (hsCRP) (mg/dL)} + \text{Patient Assessment of Pain Severity (numeric rating scale [NRS], 0 - 10)} + \text{Physician Global Assessment of Disease Activity (NRS, 0 - 10)} + (\text{morning stiffness duration [MST] in minutes} \times 0.1) + \text{elevation of upper limbs (EUL) (scale of 3 - 0)}$
- Time to disease flare defined as  $\text{PMR-AS} \geq 9.35$
- Achievement of  $\text{PMR-AS} < 1.5$
- Achievement of  $\text{PMR-AS} < 7$
- Achievement of  $\text{ESR} \leq 30 \text{ mm/h}$  at Week 24
- Achievement of  $\text{hsCRP} \leq \text{upper limit of normal (ULN)}$  at Week 24
- Change from Baseline in hsCRP
- Change from Baseline in PMR-AS
- Change from Baseline in MST
- Change from Baseline in EUL
- Change from Baseline in Physician Global Assessment of Disease Activity NRS
- Change from Baseline in Patient Assessment of Pain Severity NRS
- Change from Baseline in Patient Assessment of Stiffness Severity NRS
- Change from Baseline in Functional Assessment of Chronic Illness Therapy-Fatigue (FACIT-Fatigue)
- Change from Baseline in Health Assessment Questionnaire Disability Index (HAQ-DI)

- Change from Baseline in Patient-Reported Outcomes Measurement Information System (PROMIS) Item Bank v 1.0 – Sleep Disturbance
- Change from Baseline in Patient Assessment of Bruising Severity NRS
- Change from Baseline in EuroQol 5-dimension questionnaire, 5-level (EQ-5D-5L)
- Change from Baseline in Physician Assessment of Bruising Severity NRS
- For subjects participating in the Wearable Device Substudy:
  - Change from Baseline in the following sleep parameters: total sleep time, wake after sleep onset, sleep efficiency, and sleep onset latency
  - Change from Baseline in upper limbs range of motion (UL-ROM)

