### **Baseline PMR Disease Characteristics**

- High sensitivity c-reactive protein (hs-CRP) (mg/L)
- Erythrocyte sedimentation rate (ESR) (mm/h)
- Patient Assessment of Pain Severity Numeric Rating Scale (NRS)
- Physician Global Assessment of Disease Activity NRS
- Morning Stiffness (MST) Duration
- Elevation of Upper Limbs (EUL)
- Polymyalgia Rheumatica Activity Score (PMR-AS)
- Polymyalgia Rheumatica Activity Score (PMR-AS) (< 1.5, ≥ 1.5 and < 7, ≥ 7 and < 17, or ≥ 17)
- Patient Assessment of Stiffness Severity NRS
- Functional Assessment of Chronic Illness Therapy-Fatigue (FACIT-Fatigue)
- Health Assessment Questionnaire Disability Index (HAQ-DI)
- Patient-Reported Outcomes Measurement Information System (PROMIS) – Sleep Disturbance
- Patient Assessment of Bruising Severity NRS
- EuroQol 5-dimension questionnaire, 5-level (EQ-5D-5L)
- Physician Assessment of Bruising Severity NRS

- Rheumatoid factor (Positive ( $\geq 14$  IU/mL), Negative ( $< 14$  IU/mL))
- Time since most recent PMR flare prior to Baseline ( $\leq 12$  weeks,  $> 12$  weeks)

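### Time to PMR-AS ≥ 9.35 can count a subject who was already above the threshold at Baseline as a new flare, even if unchanged or improved (minor)

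*SAP*

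**What the plan says.** SAP 3.3 and protocol 3.4 list two PMR-AS flare endpoints among the additional efficacy endpoints. One is relative: "Polymyalgia Rheumatica Activity Score (PMR-AS) increased from Baseline by" 6.6 or more. The other begins "Time to disease flare defined as" and sets an absolute PMR-AS of 9.35 or more, with no change-from-Baseline condition.

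SAP 9.5 applies the methods already described to the additional endpoints. SAP 9.1 fixes the analysis set: "All efficacy analyses will be conducted in the ITT Population in each period". For all time-to-event endpoints it adds that "a flare at Baseline will not be counted as an event". Nothing further is said about a subject who already meets the definition at Baseline.

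Protocol 5.1 contains no PMR-AS limit. Criterion 6 requires "Clinical diagnosis of PMR and fulfillment of the 2012 EULAR/ACR provisional classification criteria for PMR". Criterion 9 is the nearest limit on disease activity: "Subject must not exhibit clinical signs and symptoms of PMR" within 2 weeks of Baseline. It is a clinical judgement about PMR, not a score. SAP 7.1 plans to tabulate Baseline values as "Polymyalgia Rheumatica Activity Score (PMR-AS) (< 1.5, ≥ 1.5 and < 7, ≥ 7 and < 17, or ≥ 17".

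**The concern.** A time-to-flare endpoint should record the change from a non-flaring to a flaring state. With an absolute threshold this works only if every subject in the risk set starts below it, and the plan does not ensure that. Cancelling the event at Baseline without removing the subject from the risk set moves the same finding to the next assessment.

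The other flare definitions are protected. A rise of 6.6 cannot be present at Baseline, where the change is zero. The primary flare needs PMR signs and symptoms plus a required glucocorticoid increase, and criterion 9 bars those signs at entry. PMR-AS has no attribution step: pain, stiffness minutes, arm elevation and hsCRP count whatever their cause.

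At stake is the reading of this one endpoint. Week 4 events that reflect Baseline status would lower the early Kaplan-Meier estimates in every arm and pull the hazard ratio toward 1.

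**Working it through.** **1. Can an eligible subject exceed 9.35?** The formula in SAP 3.3 is hsCRP (mg/dL) + pain NRS + physician global NRS + 0.1 × morning stiffness (min) + EUL. With hsCRP 0.5, pain 4, physician global 2, stiffness 30 min and EUL 0:

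0.5 + 4 + 2 + 3.0 + 0 = 9.5, which is at least 9.35.

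No numerical entry limit rules this out. Whether such a subject passes criterion 9 depends on the investigator's judgement of the cause.

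**2. What do the rules do with that subject?** The first scheduled post-Baseline visit with the full score is Week 4, as read from the EUL, physician global and hsCRP rows of the activity schedule (protocol Appendix F).

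| Baseline → Week 4 | Absolute (≥ 9.35) | Relative (rise ≥ 6.6) |
|---|---|---|
| 9.5 → 9.5 | flare | no flare (change 0) |
| 12 → 10 | flare | no flare (change −2) |
| 9.5 → 9.0 | no flare at Week 4 | no flare (change −0.5) |

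**3. The plan's own figure.** SAP 2.4 assumes 70% (highest dose) and 30% (placebo) flare-free at Week 36. Under exponential times HR = ln(0.7)/ln(0.3) = 0.296, as stated. With 37 events at two-sided 0.1, Schoenfeld power is Φ(½√37 × |ln 0.296| − 1.645) = Φ(3.70 − 1.645) = 0.98, consistent with the stated figure of more than 90%. These rates describe the investigator-defined flare and are borrowed below only to show scale.

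**4. Illustration of dilution.** Set-up: exponential flare times with hazards −ln(0.3)/36 and −ln(0.7)/36 per week, 4-weekly visits, censoring at Week 24, 20,000 simulated subjects per arm, Cox model with Efron ties. A share p of each arm is at or above 9.35 at Baseline. Those still there at Week 4 are events at Week 4; the rest are given ordinary flare times. Simulation error is about 0.01.

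| p (assumed) | HR if all stay ≥ 9.35 | HR if half in each arm fall below |
|---|---|---|
| 0 | 0.29 | 0.29 |
| 5% | 0.35 | 0.32 |
| 10% | 0.39 | 0.35 |
| 20% | 0.48 | 0.39 |

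If half the active subjects but no placebo subjects fall below, the HR is about 0.31, 0.32 and 0.35 for p = 5%, 10% and 20%.

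The Week 4 event-free proportion without such subjects is 0.3^(4/36) = 0.875 on placebo and 0.7^(4/36) = 0.961 on active. With p = 10%, all staying above, these become 0.9 × 0.875 = 0.787 and 0.9 × 0.961 = 0.865. In a 40-subject arm each such event is 1/40 = 2.5 percentage points.

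**5. Power at the planned size.** With 40 per arm, an unstratified log-rank test at two-sided 0.1, 3,000 runs and all such subjects staying above threshold:

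| p (assumed) | Counted as Week 4 events | Restricted to Baseline < 9.35 |
|---|---|---|
| 0 | 95% | 95% |
| 5% | 91% | 93% |
| 10% | 87% | 93% |
| 20% | 77% | 89% |

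Under the restriction the HR stays at about 0.29 to 0.30.

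**The case against.** The strongest reply concerns importance. This is one of about 20 additional endpoints. Overall Type I error control is not planned, and no stated decision rule or sample-size figure uses it. The ≥ 6.6-rise endpoint and change from Baseline in PMR-AS are analysed alongside, and Baseline PMR-AS is tabulated by arm. Criterion 9 bears indirectly on the pain, stiffness and arm-elevation items, and the exclusions for active infection, active fibromyalgia and inflammatory arthritis remove major non-PMR causes of a high score. All of this stands and is why the point is minor. It does not change how the written rule scores a subject at 9.5 on both visits.

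Four stronger readings are tempting, and the documents do not support them:

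- A reader might infer from the Baseline bands of 7 to below 17 and of 17 or more that the SAP expects such subjects. Tabulated bands do not show that: SAP 7.1 also has a Baseline glucocorticoid band above 15 mg/day, although criterion 23 limits the dose to 5 to 15 mg/day.
- A reader might infer that every subject above threshold at Baseline becomes a Week 4 event. The score must still be at least 9.35 then.
- A reader might take the endpoint as an objective check on the primary flare. Neither document says so, and PMR-AS includes patient-reported items and a physician rating.
- A reader might take the upper hazard ratios as an expected bias. They assume that every such subject in both arms stays above threshold.

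**Conclusion.** The defect holds, at minor severity. It follows from the written rules and needs no assumption about frequency: for this endpoint, an ITT subject at or above 9.35 at Baseline and still there at Week 4 is scored as flaring without having worsened. Randomisation balances such subjects in expectation, so the consequence is mainly dilution and lost power, not a bias favouring one arm.

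The size cannot be established from the documents, because they give neither p nor the proportion staying above threshold. The illustrative range, for p from 5% to 20%, is an HR of 0.35 to 0.48 if all stay and 0.32 to 0.39 if half in each arm fall below, against 0.29 with none. It rests on borrowed flare rates, exponential times and a Week 24 cut. Criterion 9 suggests that the lower values of p are more plausible.

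**What to change.** In SAP 3.3 or 9.1 state, before unblinding, that time to PMR-AS ≥ 9.35 is analysed in ITT subjects with Baseline PMR-AS below 9.35, and that the number excluded is reported by arm. No new data are needed.

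The cost is a departure from the all-ITT rule for one additional endpoint and the loss of what should be a few subjects. They are selected on a pre-randomization value, so the arms remain comparable. Leaving the choice until after unblinding would make it post hoc.

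Requiring a fall below 9.35 before a later value can count is not recommended. It makes eligibility for an event depend on post-randomization response: a subject who never improves could never flare and would be carried as event-free, while a responder would become eligible for an event. If the drug works, that would favour placebo.
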